7.2 Duration of Intervention and Study

Participants will complete a total of 12 study visits (including baseline assessment and follow-up assessments) as shown in **Figure 1**. Medication sessions with intramuscular ketamine will occur weekly for eight weeks. Participants will meet virtually or in person for follow-up 1, 2, 4, and 8 weeks following final medication session.

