7.3 Schedule of Assessments

The instruments to be used are standardized, have good psychometric properties, and are widely used. The schedule of study assessments is provided in **Table 1**.

Table 1: Schedule of Assessments

Instrument Name	Purpose	TIME POINT		
		BL (Wk 0)	Tx 1-8 (Wk 1-8)	Follow-up (Wk 9, 10, 12, 16)
Self-Reports and Consents				
Informed Consent	Obtain informed consent	X		
Demographics Form	Sample characterization	X		
Beck Depression Inventory-II	Self-reported assessment of depression symptom severity	X	X	X
Visual Analog Scale (VAS)	Measure subjective levels of opioid craving	X	X	X
General Anxiety Disorder (GAD-7)	Self-report of anxiety symptom severity	X	X	X
Mystical Experiences Questionnaire (MEQ)	Measure of perceptual experiences		X	
Brief Pain Inventory	Measure of pain and quality of life	X	X	X
Insomnia Severity Index (ISI)	Assess insomnia and sleep quality	X	X	X
Five Facets of Mindfulness (FFMQ)	Assess aspects of mindfulness related	X	X	X
PTSD Checklist (PCL-5)	Measure of PTSD symptoms	X	X	X
Fagerstrom Test of Nicotine Dependence (FTND)	Measure of nicotine dependence	X	X	X
Timeline Follow-Back (TLFB)	Measure of substance use	X	X	X
Clinician Assessments				
History and Physical Exam	Eligibility assessment	X		
Vital Signs Measurement	Obtain readings of blood pressure, pulse, temperature, respirations and pulse oximetry	X	X*	
Montgomery-Asberg Depression Rating Scale (MADRS)	Primary Outcome: Clinician assessed measure of depression symptom severity	X	X	X
Pre-screening Questionnaire	To assess for basic eligibility criteria before completing a full baseline visit.	X		
Laboratory and Procedural Tests				
Urine Pregnancy Test (female subjects only)	Eligibility assessment	X	X	
Urine Drug Screen	Assessment of illicit drug use	X	X	
Electrocardiogram (ECG; subjects on methadone only)	Assessment of cardiac function	X		

* Vital signs (blood pressure, pulse, respiratory rate, and pulse oximetry) will be obtained prior to treatment sessions and at 60 minutes post-treatment. Temperature will be monitored immediately prior to treatment. If there is an increase in systolic or diastolic blood pressure >30 mm Hg from baseline, or an increase in pulse rate >30 bpm from baseline, subjects will be treated with standard of care antihypertensive medications (i.e. clonidine) and the measurements will be repeated every 20 minutes until BP and pulse are within 30 points of the baseline values.

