7.5 Intervention Visit Procedures

Prior to administration of the study compounds, participants will complete self-report questionnaires and clinical assessments. The study physician will disinfect the subject's shoulder using an alcohol wipe, and the study physician will then administer the medication by intramuscular administration into the participant's deltoid muscle. Vital signs will be monitored prior to treatment, and at 60 minutes post-treatment. If during the post-administration observation period, ketamine administration causes an increase in systolic or diastolic blood pressure >30 mm Hg from baseline, or an increase in pulse rate >30 bpm from baseline, the subject will be treated with standard of care antihypertensives (i.e. clonidine), and repeat vital sign measurements will be taken approximately every 20 minutes until blood pressure and pulse are within 30 points of baseline values. Standard of care antihypertensive medications will be procured via intrainstitutional transfer from MUSC investigational drug services pharmacy distribution center. They will be stored in a DHEC compliant locked box within a locked room accessible only to study team members. If the subject experiences symptoms of hypertensive emergency, the subject will not receive further administration of ketamine and will be withdrawn from the study. After completion of the injection, participants until returned to baseline per clinical assessment which time they will undergo debriefing and complete assessments of their perceptual experience of the intervention. We will evaluate the effects of a weekly interventions for 8 sessions. Participants will return for follow-up assessment 1, 2, 4 and 8 weeks following final medication session. Follow-up visits may be conducted by telehealth.

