10.0 WITHDRAWAL OF SUBJECTS

All potential participants will be thoroughly screened for eligibility after completing informed consent. The PI may withdraw subjects from participation at any time if the participant demonstrates or reports significant distress, is felt to be at risk of harm to themselves or to others, or is otherwise unable to complete the study protocol. Referrals to university and community resources will be made as indicated for all participants withdrawn from the study. The trial will be stopped under any of the following conditions: 1) there is clear evidence of harm; 2) there is no likelihood of the intervention demonstrating benefit, or 3) there is overwhelming evidence of the benefit of the intervention.

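### Withdrawal from the study, including withdrawal for tolerability events, is followed only by referral, so later MADRS, craving, substance-use and new non-fatal AE data of withdrawn participants can be lost

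*Combined protocol and SAP*

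**What the plan says.** Section 7.5 gives one rule for symptoms of hypertensive emergency: "the subject will not receive further administration of ketamine and will be withdrawn from the study". Dosing and study participation end together.

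Other sections add reasons for withdrawal:

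- Section 10.0: "The PI may withdraw subjects from participation at any time if the participant demonstrates or reports significant distress". It extends this to risk of harm and to inability to complete the protocol.
- Section 9.0: pregnancy, or the participant's best interests.
- Section 11.4: reported illicit ketamine use between sessions. The text does not say whether the withdrawal is from ketamine or from the study.

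The step that follows is stated in Section 10.0: "Referrals to university and community resources will be made as indicated for all participants withdrawn from the study". Section 11.4 likewise names referral. No section schedules an early-termination visit or any outcome assessment after withdrawal.

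Section 7.2 sets follow-up: "Participants will meet virtually or in person for follow-up 1, 2, 4, and 8 weeks following final medication session". Table 1 in Section 7.3 heads the same visits "Follow-up (Wk 9, 10, 12, 16", which are calendar weeks. On adverse events, Section 9.0 and the first paragraph of Section 8.4 require follow-up until resolution. The second paragraph of Section 8.4 also lets it end when the person leaves the study.

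**The concern.** Aim 2 (Section 1.4) is to explore tolerability, including adverse effects, cravings and relapse. Hypertensive emergency, marked distress and illicit ketamine use are tolerability or substance-use events. What happens to mood, craving and drug use afterwards in those participants is part of what Aim 2 is meant to describe, and the later MADRS scores bear on Aim 1. Here the stated consequence of the event is what stops data collection. Data not collected after exit cannot be recovered at analysis. With about 10 participants planned (Section 5.4), one person is about 10% of the sample.

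**Working it through.** **1. The withdrawal rules side by side**

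| Trigger | Section | Stated consequence | Outcome assessment afterwards |
|---|---|---|---|
| Symptoms of hypertensive emergency | 7.5 | No more ketamine, and out of the study | None stated |
| Distress, risk of harm, unable to complete | 10.0 | PI may withdraw; referral as indicated | None stated |
| Pregnancy, best interests | 9.0 | Withdrawal by PI (Section 10.0 referral applies) | None stated |
| Illicit ketamine use | 11.4 | Withdrawn and referred | None stated |
| Worsening depression or opioid use alone | 9.0, 11.4 | Referral | Withdrawal not required |

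The last row lies outside the gap.

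**2. MADRS points at stake**

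Inputs: 8 weekly sessions and 4 follow-up visits (Sections 7.2, 7.3 and 7.5), with MADRS at each (Table 1). Section 7.2 also says "Participants will complete a total of 12 study visits", whereas its parts give 1 + 8 + 4 = 13. The count below uses only the 8 sessions and 4 follow-ups, on which the three sections agree.

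Timing: Section 7.5 says "Prior to administration of the study compounds, participants will complete self-report questionnaires and clinical assessments". I infer that MADRS is rated before the injection, since Table 1 gives no within-visit timing. The session 1 rating then precedes any drug, and a full course yields 7 (sessions 2 to 8) + 4 = 11 points after the first dose.

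For a last dose at session k:

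- withdrawal ends all assessment: k − 1 points
- only the four follow-up visits are kept: (k − 1) + 4 = k + 3 points
- all scheduled assessments continue: 11 points

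| Last dose | Exit ends assessment | Follow-up visits only | Full schedule | Lost on exit (12 − k) |
|---|---|---|---|---|
| Session 1 | 0 of 11 | 4 of 11 | 11 of 11 | 11 |
| Session 4 | 3 of 11 | 7 of 11 | 11 of 11 | 8 |

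If MADRS were rated after dosing, exit would leave k of 12 points: 1 or 4.

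**3. Does the follow-up rule settle the matter?**

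Counted from a participant's own last session in week k, the visits fall at weeks k + 1, k + 2, k + 4 and k + 8:

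- last dose at session 1: weeks 2, 3, 5, 9; shared with Table 1 (9, 10, 12, 16): week 9 only
- last dose at session 4: weeks 5, 6, 8, 12; shared with Table 1: week 12 only

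The two schedules agree for someone dosed through session 8 and share one week of four in these two early-stopping cases. Neither text says which applies to an early stopper, or whether a withdrawn participant is due a visit at all.

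**4. How often?**

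The plan gives no withdrawal rate. With 10 participants and an assumed rate p, the chance of at least one withdrawal is 1 − (1 − p)^10: 40% at p = 5%, 65% at 10%, 89% at 20%. These rates are assumptions that show a range, not forecasts.

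**The case against.** Withdrawal from the study ordinarily means that participation ends, so Section 7.5 is arguably a deliberate choice and not an omission. Someone who stops dosing without being withdrawn (Section 8.4 mentions discontinuing the intervention as part of adverse event assessment) can be read as covered by follow-up after the final medication session. That stands, and it confines the point to withdrawn participants. A reader might infer that every early stopper is lost to follow-up; the documents do not say so.

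A reader might also infer that relapse removes people from the data. It does not: Sections 9.0 and 11.4 prescribe referral for new or worsening use and for worsening depression, and substance use is assessed at every visit. The triggering events themselves are seen or reported before exit. Several withdrawals are at the PI's discretion. Serious event outcomes and deaths to 30 days after termination are pursued under Section 8.4, and acute effects are monitored under Sections 9.0 and 11.2. What remains exposed on adverse events is new non-fatal events and non-serious events still open at exit. For the open events the documents conflict and do not clearly permit loss.

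Finally, the counts in the working are of visits, not of impact. This is a small, open-label, single-arm preliminary study, so there is no between-group comparison to bias. The non-completion in the imipramine trial cited in Section 1.2 (84 of 137 completed) concerns a different drug and a different definition, and is no guide to withdrawals here. These limits narrow the point. They do not answer why data collection should stop for consenting participants who leave treatment after a tolerability event.

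**Conclusion.** The point holds for participants withdrawn under Sections 7.5, 9.0, 10.0 and 11.4. As written, their later MADRS, craving, TLFB and new non-fatal adverse event data can be lost. If exit ends assessment, a participant last dosed at session 1 or 4 supplies 0 or 3 of 11 MADRS points after the first dose. That rests on MADRS being rated before the injection and on withdrawal being taken to mean the end of assessments.

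It is tempting to go further and say that the MADRS results will look too favourable. The documents do not support that: they give no withdrawal rate and no information on how withdrawn participants would score, so neither direction nor size can be derived. The point is a worthwhile and cheap improvement, and does not invalidate the design.

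**What to change.** Leave the criteria for stopping ketamine and the PI's authority to end participation as they are.

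1. In Sections 7.5, 10.0 and 11.4, distinguish stopping ketamine from leaving the study. For participants who stop ketamine, continue the scheduled MADRS, craving, TLFB and adverse event assessments unless consent is withdrawn or the PI judges further assessment not to be in the participant's interest. Section 11.3 notes that questionnaires can themselves distress.
2. Settle with the IRB whether assessments may continue after a pregnancy, given that Section 6.4 excludes pregnant women.
3. State that the follow-up visits apply to early stoppers, and reconcile the anchor in Sections 7.2 and 7.5 with the fixed weeks in Table 1. Table 1 weeks would keep scores at common study weeks; counting from the last dose would keep time since dosing comparable.
4. Reconcile the adverse event follow-up end points in Sections 8.4 and 9.0.

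Cost: wording, plus 4 added assessments per early stopper (follow-up only) up to 11 (full schedule after a session 1 stop). Four follow-up payments come to 4 × $15 = $60 (Section 11.7), the same as for a completer. Section 7.5 already says "Follow-up visits may be conducted by telehealth"; remote assessment in place of missed treatment visits would need an added sentence. The drawbacks are that some later data will reflect other care, and that participants who withdraw consent or whom the PI removes from assessment will still be missing.

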8.0 DATA MANAGEMENT

8.1 Data Analysis Plan

Baseline demographic characteristics will be collected, and descriptive statistics will be used to characterize participants. Data will be collected and managed using the secure REDCap (Research Electronic Data Capture) database.

8.2 Data Confidentiality Procedures

We will take rigorous precautions to maintain confidentiality for all participants, using procedures that the PI and his mentors have successfully employed in similar previous, as well as ongoing related studies. All study data related to mental health outcomes (i.e., the participant responses to questionnaires) and demographics will not have any unique identifying data attached. There will be only one master list of participants (not linked to participant responses). This list will be kept locked separate from other data and will be available only to the PI, his mentors, and approved study personnel. All data will be confidentially stored (i.e., in locked files or on encrypted servers) so as to protect the confidentiality of participant information. Access to research records (paper and computerized) will be restricted to the project staff, and to sponsor audit personnel and MUSC IRB auditors when indicated. All study personnel have completed (or will complete upon hiring) a certified program of instruction in the protection of human subjects in research, such as the University of Miami CITI course. These courses in the responsible conduct of research and the protection of human subjects will be completed on an annual basis, in compliance with MUSC regulations.

8.3 Data Quality Control Procedures

Data quality will be monitored by random inspection of the completed forms by the study team and any irregularities or problems detected will be discussed with the PI.

8.4 Study Documentation and Data Handling

Any clinical study event that is judged to be an AE will be recorded on the AE form during the course of the study. The PI and/or trained Research Assistant will ensure this information is captured during every study visit. Whenever a study participant has reported an AE, the study coordinator will discuss the event immediately with the PI (if possible while the study participant is there) who will evaluate the event. If the AE is not serious, the information will be recorded, managed medically as appropriate, and the event will be followed until resolution. SAEs will also be recorded on the AE Form, managed medically as appropriate, and the event is followed until resolution. In addition, the PI will review all completed AE forms for determination of SAE. All SAE reports will be sent to the MUSC IRB within 24 hours of learning of event occurrence.

AEs/SAEs will be documented and reported as per IRB requirements. Research staff will identify AEs and obtain all available information to assess severity, seriousness, study relatedness, expectedness, outcome and the need for change or discontinuation in the study intervention. Adverse events will be documented on AE Logs and additional relevant AE information, if available, will be documented in a progress note in the research record as appropriate to allow monitoring and evaluating of the AE. If the AE meets the definition for Serious, appropriate SAE protocol specific reporting forms will be completed and disseminated to the appropriate persons and within the designated timeframes as indicated above. For each AE/SAE recorded, the research staff will follow the AE/SAE until resolution, stabilization or until the participant is no longer in the study. When a reportable SAE is identified, the research assistant will initiate an SAE form, and the following individuals will be notified within 24 hours of the site's initial notification of the SAE:

1. The PI ([name]) will provide oversight, consultation, assessment, and documentation as appropriate of the SAE.
2. The research staff will notify the MUSC IRB, and complete the AE report form in conjunction with the PI. Communication with the MUSC IRB is through email, memos, official IRB forms, and online reporting.

If complete information is not available when the initial 24-hour SAE report is disseminated, follow-up information will be gathered to enable a complete assessment and outcome of the event. This information may include hospital discharge records, autopsy reports, clinic records, etc. The research staff will attach copies of source documents to the SAE report for the PI and for forwarding to the sponsor as appropriate. All deaths that occur during the study or 30 days post termination from the study are required to be reported as adverse events even if they are expected or unrelated. Other adverse events are reportable to the MUSC IRB if the AE is unexpected AND related or possibly related AND serious or more prevalent than expected. All three criteria must be met for an AE to be reported to the MUSC IRB. The IRB definition of unexpected is that the AE is not identified in nature, severity or frequency in the current protocol, informed consent, investigator brochure or with other current risk information. The definition of related is that there is a reasonable possibility that the adverse event may have been caused by the drug, device or intervention.

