1.4 Specific Aims

To achieve these objectives, the following Specific Aims are proposed:

Specific Aim 1: To preliminarily explore the efficacy of ketamine-assisted psychotherapy in reducing symptoms of depression using the Montgomery Asberg Depression Rating Scale (MADRS).

Specific Aim 2: To preliminarily explore the tolerability of ketamine-assisted psychotherapy in treatment of depression including adverse effects, cravings and relapse

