3.3 Study Drug, Dose, Mode of Administration and Justification

Ketamine is concentrated at a dose of 100 mg/ml and will be administered by intramuscular administration in the amount of 0.5 mg/kg with plan to flexibly titrate by 0.25 mg/kg each session based on tolerability to a maximum weight-based dose of 1.5 mg/kg. Total dose on a given day will be limited to 60 mg regardless of subject's weight. While formal dose response studies for depression are lacking, ketamine has been most widely studied for psychiatric indications at 0.5 to 1.0 mg/kg given intravenously. Recent studies have shown that intramuscular ketamine may be as effective as intravenous ketamine for depression and may be more practical clinically (Chilukuri et al., 2014; Xu et al., 2016). Although there are only a few studies evaluating the use of ketamine in the treatment of substance use disorders, doses in these trials have ranged from 0.5 to 0.8 mg/kg given intravenously or 2 mg/kg given intramuscularly (Jones, Mateus, Malcolm, Brady, & Back, 2018). When given intramuscularly, ketamine has a peak time of 5-30 minutes following injection and a bioavailability of 86-97% (Grant, Nimmo, & Clements, 1981). Of note, ketamine elimination clearance is high with a half-life of 2-3 hours and clearance in women that is up to 20% higher than men (Mion & Villeveille, 2013).

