11.3 Psychological Risks

Ketamine commonly causes transient dissociation (including derealization and depersonalization) and perceptual changes (e.g. distortion of time and space, sense of illusions). Based on prior studies these effects occur in 42% of subjects receiving ketamine. Anxiety occurs in 15% of subjects receiving ketamine. Psychological distress will be minimized with pre-treatment relaxation exercises and psychological reassurance as needed. Psychological distress will be minimized with pre-intervention relaxation exercises and reassurance as needed. In prior trials with ketamine for depression, these measures are sufficient to manage dissociation and anxiety in the overwhelming majority of participants. However, standard of care medications for agitation (e.g. benzodiazepines) will be available in the event that participants develop severe anxiety psychological distress unmitigated by reassurance and relaxation exercises. Psychiatric hospitalization will be arranged if needed, in the unlikely event of severe or prolonged psychiatric symptoms (e.g. lasting greater than four hours or the business day). Participants may also have emotional distress from answering the questionnaires, although this is mild in the investigators' experience with these instruments.

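### Adverse effects are part of Specific Aim 2, but the known transient ketamine effects have no solicited query, AE definition or planned summary, so their recording may be incomplete and uneven

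*Combined protocol and SAP*

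**What the plan says.** Section 1.4 states Specific Aim 2 as "To preliminarily explore the tolerability of ketamine-assisted psychotherapy in treatment of depression including adverse effects, cravings and relapse". Section 1.3 also puts tolerability in the primary objective. Section 3.3 plans to "flexibly titrate by 0.25 mg/kg each session based on tolerability".

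Section 8.4 sets out how adverse events are collected:

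- The entry rule is "Any clinical study event that is judged to be an AE will be recorded on the AE form during the course of the study".
- On frequency: "The PI and/or trained Research Assistant will ensure this information is captured during every study visit".
- On content: "Research staff will identify AEs and obtain all available information to assess severity, seriousness, study relatedness, expectedness, outcome".
- On mild events: "If the AE is not serious, the information will be recorded, managed medically as appropriate, and the event will be followed until resolution".
- Expectedness acts as a filter in one place only, reporting to the IRB: "Other adverse events are reportable to the MUSC IRB if the AE is unexpected AND related or possibly related AND serious". The sentence goes on to allow greater-than-expected prevalence in place of seriousness.

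Section 11.1 introduces the effects in 11.2 and 11.3 as adverse reactions. Section 11.2 gives about 16% for sedation and 29.8% for a transient blood-pressure rise. On dissociation and perceptual change, 11.3 says "Based on prior studies these effects occur in 42% of subjects receiving ketamine", and it gives 15% for anxiety. Nausea and vomiting appear only in section 9.0, as a reason for fasting before sessions.

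Table 1 (section 7.3) has no row for adverse events and no dissociation or sedation scale. Section 8.1 plans descriptive statistics for baseline characteristics and nothing for adverse events.

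**The concern.** Whether a known effect enters the data depends on someone deciding that it is an adverse event, and the plan gives no definition, standard question, list of effects or severity scale to guide that decision. The difficulty is sharpest for perceptual change. Section 11.3 lists it as a risk, while section 7.1 builds the therapy partly around supporting the participant through the acute drug experience and reflecting on it afterwards. Two competent staff members could record the same session differently.

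The team that decides is also the team that treats. Section 14.0 has the principal investigator or a co-investigator give the drug, and section 9.0 makes the principal investigator responsible for assessing adverse effects.

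At stake is the adverse-effect part of Aim 2. If mild, transient effects are noted in some sessions and not in others, the resulting rates are hard to interpret. They also leave no uniform record of the tolerability on which each dose step rested. Effects not asked about at the time cannot be recovered later.

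**Working it through.** The plan derives no adverse-event rate, sample size or precision figure, so there is nothing of its own to reproduce. The check has two parts.

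**1. What would capture each named effect if no one judged it to be an AE?**

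| Effect (section) | Scheduled measure | Does it record the adverse effect? |
|---|---|---|
| Dissociation or perceptual change (11.3) | Mystical Experience Questionnaire after dosing (4.3, 7.3) | Touches perceptual change, but scores it as a mystical experience, not as an adverse effect |
| Acute anxiety (11.3) | GAD-7 at each visit (7.3) | No: section 7.5 has the self-report questionnaires completed before dosing |
| Sedation (11.2) | Ongoing observation by staff | Watched, but no rating or form entry is specified |
| Nausea or vomiting (9.0) | None | No |
| Injection-site reaction (11.2) | None | No |
| Blood-pressure rise (11.2) | Vital signs before dosing and at 60 minutes (7.3, 7.5) | Yes, though the scheduled reading comes after the 40-minute average peak cited in 11.2; that section also mentions routine monitoring during treatment |

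Cravings and relapse, the rest of Aim 2, are covered by the craving scale, Timeline Follow-Back and urine drug screens. The gap is confined to adverse effects other than vital signs.

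**2. How sensitive is a result in 10 participants?**

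Inputs: N = 10 (section 5.4); p = 0.42 and 0.15 (11.3), 0.16 (11.2), and 0.117 (3.2, for closely overlapping perceptual effects). The share c of affected participants whose effect is recorded is not given anywhere. Values from 100% down to 25% are assumptions for illustration, not estimates.

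Expected number recorded = N × p × c. Chance that none is recorded = (1 − p × c)^10.

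| Effect | c = 100% | c = 50% | c = 25% |
|---|---|---|---|
| Dissociation, p = 0.42 | 4.2; 0.004 | 2.1; 0.095 | 1.05; 0.33 |
| Same effects at p = 0.117 | 1.17; 0.288 | 0.59; 0.547 | 0.29; 0.743 |
| Sedation, p = 0.16 | 1.6; 0.175 | 0.8; 0.434 | 0.4; 0.665 |
| Anxiety, p = 0.15 | 1.5; 0.197 | 0.75; 0.459 | 0.38; 0.682 |

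Each cell shows the expected number recorded, then the chance of none. For example, anxiety at c = 50% gives 10 × 0.15 × 0.5 = 0.75 and (1 − 0.075)^10 = 0.459.

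Exact (Clopper-Pearson) 95% intervals with n = 10 are 0% to 30.8% for 0 cases, 2.5% to 55.6% for 2, and 12.2% to 73.8% for 4. One missed participant changes a proportion by 1/10, or 10 percentage points.

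**The case against.** A reader might infer that the entry rule in section 8.4 leaves expected effects out, and that the trial will therefore understate adverse effects. The documents do not support either step. Sections 11.1 and 11.2 already call these effects adverse. Section 8.4 requires capture at every visit, records non-serious events, and has expectedness assessed for each AE, which would be pointless if expected events were dropped. Requiring an event to be judged an AE is ordinary protocol wording. Reports from participants go to the principal investigator, which gives some consistency, and the AE assessment includes whether the intervention needs changing. Bias towards good tolerability is possible, but it is not shown.

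The numbers are also soft. No recording share is stated, so any calculated shortfall restates its own assumption. Section 3.2 gives 11.7% and section 11.3 gives 42% for closely overlapping effects, which moves the expected count from 1.17 to 4.2 before any under-recording. Section 11.1 says the estimates come from intravenous ketamine, whereas this trial gives eight intramuscular sessions. The exact intervals for 2 and 4 cases overlap heavily, and the plan sets no tolerability threshold that a missed case could cross. The AE form is not reproduced, so it may contain prompts that cannot be seen here.

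All of this stands, and it limits the point to unspecified ascertainment. It does not supply a definition, a standard question or an analysis, and the other scheduled measures do not fill the gap except for vital signs.

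**Conclusion.** The point holds as a weakness in how adverse effects are ascertained. Apart from vital signs, the adverse-effect part of Aim 2 rests on case-by-case judgement, with no AE definition, no solicited query for known transient effects and no planned summary. Recording of dissociation, sedation, acute anxiety and nausea may therefore be incomplete and inconsistent.

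The size and direction of any error cannot be derived from the documents. The most that can be said is that one missed participant is worth 10 percentage points and that there is no control arm to share the error. If, as an assumption, half of affected participants were recorded, the chance of seeing no anxiety case would rise from 0.197 to 0.459. That rests on the protocol's intravenous rates applying per participant and on participants being independent.

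The change should be made before enrolment, because it determines what data exist for a stated aim.

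**What to change.** - Define an AE in section 8.4 and state that expected, transient effects are recorded.
- Keep open-ended AE recording and add one fixed checklist to Table 1, covering the effects named in sections 9.0, 11.2 and 11.3: perceptual change or dissociation, sedation, anxiety, nausea or vomiting, injection-site reaction and blood-pressure rise.
- Complete it at each medication session before discharge, and at the next visit for the interval since. After the eighth session the next visit is the week 9 follow-up. Record yes or no, severity and duration, whether or not the event is judged an AE.
- In section 8.1, report the number and proportion of participants with each effect, with exact 95% intervals, as the adverse-effect result for Aim 2. Any breakdown by dose should be descriptive only, because dose is confounded with session order.
- Reconcile the 11.7% in section 3.2 with the 42% in section 11.3 before using either as a benchmark.

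The cost is a one-page form and a few minutes per visit with existing staff; 10 participants × 8 sessions gives at most 80 session checklists, plus the interval questions. Reported rates will be higher than with unsolicited recording, and the report should say so when comparing with other studies. No dose or clinical rule changes. If the AE form already has such prompts, citing them in the protocol would meet most of this.
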